Statistical Analysis Plan

Effects of mobilization dose in surgical intensive care unit patients on adverse discharge disposition

Original Date: August, 20, 2018

Table of Contents

1. Primary and Secondary Aim Overview.....	2
2. Primary aim.....	2
Hypotheses.....	2
Covariate Data.....	3
Statistical analysis.....	3
3. Secondary aim.....	5
Hypothesis.....	5
Statistical Analysis.....	5
4. Sample Size.....	6
5. Data collection.....	6

1. Primary and Secondary Aim Overview

Primary Aim

The primary aim of this study is to assess the effects of mobilization dose in critically ill patients on adverse discharge disposition (ADD) (primary outcome). The primary hypothesis of this study is that the mobilization dose in the surgical intensive care unit measured by Mobilization Quantification Score (MQS) is associated with ADD.

Secondary Aim

The secondary aim is to evaluate the association between rectus femoris cross sectional area (RFCSA) measured by bedside ultrasound within 48 hours of enrollment and mobilization dose received in the surgical intensive care unit (SICU).

2. Primary Aim

This study aim is driven by the research hypothesis that the MQS - a new method to quantify mobilization dose based on intensity and duration with more granularity than currently used mobilization quantification instruments - reflects the improving effects of early mobilization on discharge disposition.

Exposure variable

The primary exposure variable is the mean daily mobilization dose quantified by the MQS. The MQS is a newly developed score that quantifies mobilization provided by SICU nurses and physical therapists incorporating the mobilization level as well as its duration. The MQS is calculated daily throughout the SICU stay and will be divided by the number of ICU days to arrive at the exposure variable mean daily mobilization dose.

The secondary exposure variable used for comparison is the SICU optimal mobilization score (SOMS).

Primary Outcome

The primary outcome ADD is defined as discharge to facilities providing long-term care assistance for daily activities, including nursing homes and skilled nursing facilities, hospice at the patient's home, hospice in a healthcare facility, or in-hospital mortality.

Hypotheses

Primary Hypothesis

The primary hypothesis is that mobilization dose quantified via MQS predicts adverse discharge disposition.

Secondary Hypothesis

The key secondary hypothesis is that the MQS predicts ADD better than the SICU optimal mobilization score [SOMS] (Schaller et al., 2016).

We also hypothesize that the MQS predicts ICU length of stay, hospital length of stay, functional independence measure (mmFIM) at ICU and hospital discharge, 3-month mortality, change in muscle mass quantified by change in RF-CSA, ICU coma- and delirium-free days, ICU ventilator-free days, ICU vasopressor-free days, ICU neuromuscular blocking agent free days, opioid dosage, corticosteroid days, and physical work capacity 3 months after hospital discharge quantified by the Duke Activity Status Index (DASI).

Covariate Data

Predefined confounders in multivariable adjusted analyses include APACHE2 (Knaus, Draper, Wagner, & Zimmerman, 1985), sex-adjusted rectus femoris cross sectional area (RFCSA) (Janssen, Heymsfield, Wang, & Ross, 2000) measured via bedside ultrasound upon admission, and the Risk Quantification Index for 30-day Postoperative Morbidity (PSS morbidity) (Dalton et al., 2011).

RFCSA measured by bedside ultrasound has been shown to be an independent predictor of adverse patient outcomes (Mueller, Eikermann 2016).

RFCSA will be adjusted for sex using published skeletal muscle mass values of the lower body of healthy adults (Janssen et al., 2000). Thus, RFCSA of female patients are multiplied with the coefficient 1.484, whereas male patients represent the reference group (adjustment coefficient 1). Sex-adjusted RFCSA will be used for further statistical analyses.

Statistical Analysis

All analyses are performed prospectively with prespecified endpoints and statistical methods.

Primary analysis

Unadjusted Analysis: We will conduct univariate logistic regression analysis to investigate the association between mobilization dose quantified by MQS and ADD.

Adjusted analysis: Multivariable logistic regression (mean daily mobilization dose (MQS)/ ADD) analyzing whether mobilization dose predicts adverse discharge independent from the defined covariates (APACHE2, PSS Morbidity score, and sex adjusted admission RFCSA).

Secondary analyses

We will perform Net Reclassification Index and c-statistics to compare the predictive capability for ADD of the MQS to the SOMS. To further confirm the robustness of our results we will conduct Aikaike Information Criterion (AIC) and likelihood ratio test. AIC provides the relative quality of the estimated model. The likelihood ratio test compares the goodness of fit of two statistical models.

Multivariable logistic regression will be performed to evaluate the relationship between mean daily mobilization dose and other binary secondary outcomes controlling for above defined covariates. Zero truncated negative binomial regression will be used to analyze the association between mobilization dose and the secondary outcomes ICU and hospital length of stay. Negative binomial regression will be used to analyze the association between mobilization and the secondary outcomes coma- and delirium-free days, NMBA-free days, ventilator-free days, and functional independence measure (mmFIM) at ICU and Hospital discharge.

We will use linear regression to analyze the association between mobilization and physical work capacity 3 months after hospital discharge quantified by the Duke Activity Status Index (DASI) and opioids dosage (mg), if normality assumption is satisfied. Otherwise, transformation of the variables will be performed, and the transformed variables will be used as the outcome in the linear model.

Planned Sensitivity Analyses

Evaluation of confounder model: AUC-Analysis including the predefined confounders to determine the Area Under the receiver operator curve.

Categorized exposure variable: (2-quantile [high, low mobilization dose], tertiles [low, intermediate, high mobilization dose])

Alternative Exposure Variable: For each patient, mobilization data will be centered, and we will perform simple linear regression with the individual mean mobilization dose being the estimated intercept of each patient. The estimated slope from the linear regression will be considered as the change rate of mobilization dose. Two exposures will be included in our model, the slope of the mobilization dose and the intercept. We will conduct multivariable logistic analysis controlling for the same confounder variables (expected 4DoF: Intercept, Slope, APACHE2, RFCSA (continuous), PSS morbidity) from the primary analysis.

Evaluate the AUC with alternative Exposure Variable (intercept/ slope): We will compare discriminative ability of our primary model to a model with two exposure variables (intercept (mean mobilization dose for each patient) and slope) utilizing Net Reclassification Index, Brier Score and c-statistics.

Generalized propensity score: In an exploratory approach, accounting for the degrees of freedom available, we will include a generalized propensity score to reduce bias induced by discrepancies in patient characteristics. The propensity score will be generated from different covariates identified as influencing the exposure including APACHE, GCS at enrollment, ASA at admission, PSS-Morbidity, duration of ventilation, duration of sedation, duration of delirium, opioid dose, vasopressors. The propensity score will be confined for a binary exposure variable. To derive at a binary variable, we will categorize the mean mobilization dose (MQS) into two categories, high vs. low.

Subgroup analyses: We will perform a subgroup analysis in patients who received surgery upon admission to the ICU.

Planned Exploratory Analyses

We aim to explore the association of other variables that can be used to quantify mobilization intensity and duration (other than the composite exposure MQS) and adverse discharge disposition.

The additional variables used to quantify mobilization intensity and/or dose are:

- Mean highest achieved level of mobilization therapy (Daily highest achieved ICU mobilization scale level/ICU days)
- Highest achieved mobilization level using ICU mobilization score
- Mean number of daily mobilization sessions (Total number of mobilization units/ICU days)
- Mean duration of mobilization units according to MQS (Total duration of mobilization treatment based on MQS/number of sessions throughout the ICU stay)
- Fraction of days mobilized (Number of mobilization days/ ICU days)
- Early mobilization frequency (Total number of mobilization units from day 1 through 3 on the ICU)

We will use multivariable logistic regression for exploratory analyses analyzing the association between the above-mentioned variables used to quantify mobilization intensity and/or dose.

3. Secondary Aim

Exposure variable

The RFCSA assessed through bedside ultrasound measurements within 48h is used as a continuous exposure variable.

Outcomes

The outcome for the secondary aim of the study is the repeatedly measured daily mobilization dose as quantified by the MQS.

Hypothesis

Primary hypothesis

The primary hypothesis is that RFCSA is an independent predictor of mobilization dose in the SICU.

Statistical Analysis

All analyses are performed prospectively with prespecified endpoints and statistical methods.

We will conduct a generalized linear mixed effect model to analyze whether the RFCSA quantified via bedside ultrasound is an independent predictor of daily mobilization dose in the ICU.

Predefined confounders include the Barthel Index at hospital admission, APACHE2 and Charlson Comorbidity Index (CCI).

Secondary analysis

We will conduct a generalized linear mixed effect model to analyze whether the RFCSA quantified via bedside ultrasound is an independent predictor of daily mobilization dose in the ICU utilizing an alternative exposure variable. The exposure variable will be the binary variable "Sarcopenia

yes/no". Sarcopenia is quantified by RFCSA assessed through bedside ultrasound measurements within 48h. We will apply Youden's Index to define the optimal cutoff point of RFCSA for Sarcopenia. (Mueller, Eikermann 2016).

Sarcopenia is a clinical syndrome that describes progressive and generalized loss of skeletal muscle mass and strength and is associated with patient outcomes. (Delmonico, Harris, Lee, J Am Geriatr Soc, 2007)

Sample Size and Power

Based on data obtained by the same centers in the SOMS trial (Schaller et al., 2016) there is a correlation between mobilization dose and discharge disposition of 0.25. We therefore calculate that a sample size of 150 patients provides a power of >0.8 to identify a significant effect (alpha-error: 0.05) for our primary outcome.

Data collection

Data collection

On ICU admission, patients' baseline characteristics [age, sex, race, ethnicity, height, weight, admission diagnoses, Charlson comorbidity index (CCI), ASA PS, Frailty Score, Short Nutritional Assessment Score Questionnaire (SNAQ) Score reason for ICU admission] will be noted. Admission laboratory data and vital signs to calculate the APACHE II score, will be recorded as well as the severity of organ dysfunction [Sequential Organ Failure Assessment (SOFA) score]. SOFA scores will be obtained within 48 hours of SICU admission and on days when follow up ultrasound measurements are conducted (every 8 days/ at ICU discharge). Daily laboratory data, vital signs, medication and ventilation/ABG will be noted. We will further collect data at ICU discharge, Hospital discharge and 3 months after discharge. A summary of the data that we will collect is listed below.

Baseline

Medical Record Number, First name, Last name , Date of Birth, Age, Sex, Race, Ethnicity, Height, Weight at ICU admission, ICU admission [date] , Hospital admission [date], Admission category, Patient had surgery prior to inclusion (y/n) Date of surgery, Surgery CPT Code, Charlson Comorbidity Index, ASA, Frailty Phenotype Modified, Short Nutritional Assessment Questionnaire, APACHE II, Barthel Index 2 weeks prior to admission, Glasgow Coma Scale motor component at enrollment, Absence of lower extremity (y/n), Pregnancy (y/n), Procedural Severity Score.

Follow-up

Richmond Agitation and Sedation Score (RASS), SOFA score, Medical Research Council Muscle scale (MRC scale), Confusion Assessment Method for the ICU (CAM-ICU), Nutrition, Renal replacement therapy (y/n)

Mobility

MQS score, SOMS score, Physical Therapy (PT) time [mins], nonPTMobilization [mins], walking distance [feet], Rectus femoris diameter left [cm²], Rectus femoris diameter right [cm²]

Vital Signs

Systolic blood pressure, diastolic blood pressure, mean arterial blood pressure (MAP), Respiratory rate, Body temperature, Heart rate.

Laboratory

Hb [g/dL], Hk, Creatinine [mg/dL], Urine output [μ mol/L], Alb (g/dL), INR, blood Glucose [mg/dL], serum sodium (Na) [mEq], K [mEq/L], glomerular filtration rate (GFR), Bilirubin [μ mol/L], CRP, WBC count, CKD, Platelets [$\times 10^9/L$].

Medication

Sedation needed (y/n), Steroids (y/n), Opioids total dose per day [morphine equivalent dose, mg], Vasopressors (y/n), NMBAs (y/n + drug), Propofol (y/n), Total propofol dose per day.

Ventilation/ABG

Date intubated, Date extubated, Reintubation (y/n)

ICU Discharge

mmFIM score in domains transfer and locomotion, ICU Discharge [date], ICU LOS, number of PT visits, ICU Readmission, weight at ICU discharge, medical interventions during ICU stay

Hospital Discharge

Hospital Discharge [date], Hospital Readmission, Hospital LOS, In-Hospital Mortality, Discharge destination, Total costs of care

Phone Call

DASI, Readmission to any Hospital, One-month mortality, Three-month mortality.

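### The primary exposure averages MQS over the whole SICU stay while ADD includes death and hospice, so low mobilization in patients' last ICU days could bias the association, and no planned MQS analysis checks for this

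*SAP*

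**What the plan says.** **Exposure** (SAP section 2, Exposure variable). "The primary exposure variable is the mean daily mobilization dose quantified by the MQS". It is built over the whole stay: "The MQS is calculated daily throughout the SICU stay and will be divided by the number of ICU days". No fixed window, landmark or exclusion of final days is stated.

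**Outcome** (section 2, Primary Outcome). Besides discharge to long-term care facilities, ADD counts "hospice at the patient's home, hospice in a healthcare facility, or in-hospital mortality".

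**Aim and hypothesis.** The wording is mixed. Section 1 states: "The primary aim of this study is to assess the effects of mobilization dose in critically ill patients on adverse discharge disposition". Section 2 adds the research hypothesis that the MQS "reflects the improving effects of early mobilization on discharge disposition". The formal hypothesis is predictive: "The primary hypothesis is that mobilization dose quantified via MQS predicts adverse discharge disposition".

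**Adjustment** (section 2, Primary analysis). The multivariable logistic model asks whether dose predicts ADD "independent from the defined covariates (APACHE2, PSS Morbidity score, and sex adjusted admission RFCSA").

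**Other MQS analyses** (Planned Sensitivity Analyses). The SAP plans median and tertile splits of the dose, a per-patient intercept and slope, an exploratory propensity score for high versus low mean dose, and a subgroup of surgical patients. The only early-window measure is exploratory and counts sessions rather than MQS: "Early mobilization frequency (Total number of mobilization units from day 1 through 3 on the ICU").

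**The concern.** For a patient who dies in the ICU, the averaging window runs up to the outcome. For one moved to comfort care there, it includes days after the course toward the outcome was set. If mobilization falls in those days, part of the exposure is a consequence of the approaching outcome. The distortion goes in the hoped-for direction: lower mean dose among patients with ADD, hence an odds ratio below 1.

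What is at stake is the interpretation. A significant whole-stay result would be consistent with a benefit of mobilization, with terminal decline, or with a mixture. The SAP has no MQS analysis that separates them, yet its aim is worded as an effect and its rationale concerns early mobilization.

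**Working it through.** **1. The plan's own figure.** Sample Size and Power gives r = 0.25, n = 150, alpha 0.05 and power above 0.8. By Fisher z, two-sided, power = Φ(atanh(r)·√(n−3) − 1.96) = Φ(0.2554 × 12.124 − 1.96) = Φ(1.137) = 0.872. The figure reproduces. It does not depend on the exposure window, so it neither supports nor refutes the concern.

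**2. How terminal days enter the mean.** Let a patient have usual daily MQS m, T ICU days and zero MQS on the last k. The exposure becomes m(T − k)/T. With T = 9, it is 7/9 = 0.78 of m for k = 2 and 6/9 = 0.67 of m for k = 3.

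**3. Whether a planned analysis removes this.**
- APACHE2, PSS morbidity and admission RFCSA do not record later decline in the ICU.
- Median and tertile splits use the same whole-stay mean.
- In the intercept/slope model the intercept is, by the SAP's own description, the patient's mean dose, so it contains the same days. Low final days also pull the slope down.
- The propensity score models high versus low values of the same mean. Several of its covariates are durations (ventilation, sedation, delirium) with no early window stated, so time order is not restored.
- The surgical subgroup changes the patients and leaves the window as it is.

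**4. Size when dose has no effect.** All inputs here except n = 150 and the form of the model are assumptions, because the SAP gives none. Assumed: 5, 10 or 15% of patients die in the ICU; 30% of the others have ADD; stay is at least 3 days (mean about 9); patient-level MQS is log-normal (log-SD 0.6) with day-to-day log-SD 0.4. Dose is independent of outcome except that MQS is cut on the last 2, 3 or 5 days of patients who die. The three covariates are noise, so confounding plays no part. There were 400 runs per scenario and a two-sided 5% test. Results with MQS cut to zero:

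| ICU deaths | Zero days | Whole-stay: rejects | Median OR per SD | Median r | Days 1-3: rejects | Deaths excluded: rejects |
|---|---|---|---|---|---|---|
| 5% | 2 | 0.048 | 0.94 | −0.024 | 0.037 | 0.037 |
| 5% | 3 | 0.075 | 0.89 | −0.050 | 0.043 | 0.035 |
| 5% | 5 | 0.113 | 0.83 | −0.080 | 0.043 | 0.030 |
| 10% | 2 | 0.107 | 0.87 | −0.058 | 0.065 | 0.040 |
| 10% | 3 | 0.170 | 0.82 | −0.090 | 0.040 | 0.033 |
| 10% | 5 | 0.355 | 0.73 | −0.136 | 0.113 | 0.040 |
| 15% | 2 | 0.150 | 0.85 | −0.075 | 0.072 | 0.065 |
| 15% | 3 | 0.275 | 0.76 | −0.119 | 0.070 | 0.058 |
| 15% | 5 | 0.590 | 0.64 | −0.187 | 0.207 | 0.040 |

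With a 50% cut in place of zero, the whole-stay rejection rate was 0.035 to 0.180. With no terminal drop it was 0.043 (1,000 runs). Monte Carlo error around 0.05 is 1.96 × √(0.05 × 0.95/400) = 0.021, so 7 of the 18 scenarios cannot be told from nominal and 11 lie above it. The spurious correlation, 0.017 to 0.187 in absolute value, is 7% to 75% of the planning value of 0.25.

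**5. Sensitivity to the assumptions.** Further no-effect runs at n = 150 varied mean stay (7 or 10 days), between-patient log-SD of MQS (0.3 or 0.6) and the death risk at average severity (the model intercept). With two zero days, whole-stay false positives were 7-14% at a death intercept of 5%, 4-33% at 10% and 19-72% at 20%. With one zero day they were 3-6% at 5% and 10-19% at 20%. Another set gave 63% at 20% deaths with two zero days and 86% with three; there the day 1-3 landmark rejected in 2-9% of runs and the model without deaths in 2-6%.

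**The case against.** The strongest reply is that the formal hypothesis, the planned analysis and the comparison with SOMS are all about association or prediction, for which whole-stay dose is less harmful. That stands in part: the concern matters less for the hypothesis that MQS predicts ADD. It does not answer the primary aim, which speaks of effects, or the rationale, which speaks of early mobilization.

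Second, the SAP nowhere says that dying patients are mobilized less, nor how many patients die or go to hospice. This stands. The mechanism is conditional, and that the window runs up to ICU death is inferred from the whole-stay wording. With few deaths or a short or partial drop, the bias is negligible.

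Third, the mechanism does not reach discharges to nursing facilities, which are also ADD, or decline that begins after the ICU. The simulations cut MQS only before ICU death, so the hospice part is argued and not quantified. This also stands.

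A reader might infer that the primary association would be produced entirely by end-of-life days, or that the SAP treats low mobilization as a proven cause of ADD. The documents support neither. The first is a possibility under some assumptions, and the SAP's wording mixes effect with prediction.

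**Conclusion.** The concern holds in conditional form. If patients who die in the ICU or move to comfort care there are mobilized less in their last ICU days, the whole-stay mean biases the dose-ADD association away from the null in the protective direction. Neither the admission covariates nor any planned MQS analysis would remove or reveal it.

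The size is unknown. With assumed ICU death risks of 5-20%, one to three zero-MQS days before death and no true effect, the false-positive rate runs from nominal (about 5%) to above 60%. It depends on the number of deaths, length of stay and between-patient spread of MQS, none of which the SAP gives. It would be wrong to conclude that the primary analysis is invalid or must be replaced. What follows is that, as planned, it cannot by itself support a claim about an effect of early mobilization. A prespecified sensitivity analysis should be added.

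**What to change.** Keep the primary analysis. Add to Planned Sensitivity Analyses two versions of the adjusted primary model:

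- **(a)** exposure = mean daily MQS over ICU days 1-3, in patients alive and still in the ICU at the end of day 3;
- **(b)** the whole-stay exposure, with in-hospital deaths and hospice discharges excluded.

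Report odds ratios per SD with 95% confidence intervals beside the primary result. Describe the result as an effect of early mobilization only if the odds ratio in (a) has the same direction and is not materially attenuated, with the margin stated in advance. Otherwise report an association.

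**Cost.** Two extra models on daily MQS that is already collected. Analysis (a) omits patients who leave by day 3 (about 6-19% under assumed stays) and addresses early rather than whole-stay dose. It can keep some bias when terminal days overlap days 1-3, as in the two most extreme scenarios of the table (0.113 and 0.207). Analysis (b) conditions on survival and has fewer events. Under the 10% death scenario, excluding deaths alone lowers expected ADD events from 150 × (1 − 0.9 × 0.7) = 55.5 to 135 × 0.3 = 40.5. The two have different weaknesses, which is the reason to run both.

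### The mmFIM models adjust for no functional score, so an association of MQS with mmFIM at ICU discharge cannot be read as an effect of mobilization dose

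*SAP*

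**What the plan says.** **Exposure** (SAP section 2, Exposure variable). MQS is described as "incorporating the mobilization level as well as its duration". On its window: "The MQS is calculated daily throughout the SICU stay and will be divided by the number of ICU days". The averaged exposure therefore runs up to ICU discharge.

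**Outcome** (Data collection, ICU Discharge). The item recorded is "mmFIM score in domains transfer and locomotion".

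**Hypothesis** (section 2, Secondary Hypothesis). "We also hypothesize that the MQS predicts ICU length of stay, hospital length of stay, functional independence measure (mmFIM) at ICU and hospital discharge". This is one of a long list of secondary outcomes below the key secondary comparison with SOMS.

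**Model** (section 2, Secondary analyses). Negative binomial regression is planned for several outcomes, including "ventilator-free days, and functional independence measure (mmFIM) at ICU and Hospital discharge". The sentence names no covariates, lag, landmark or shortened exposure window.

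**Adjustment** (section 2). Covariate Data predefines three confounders for the adjusted analyses. The primary model is to test whether dose predicts outcome "independent from the defined covariates (APACHE2, PSS Morbidity score, and sex adjusted admission RFCSA". None of the three is a functional score.

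**Pre-admission function** (section 3, Statistical Analysis, and Data collection, Baseline). The Barthel Index is collected. It is a predefined confounder only where daily MQS is the outcome and RFCSA the exposure.

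**The concern.** A patient who can stand and walk can be mobilized to a higher level and will also score higher on transfer and locomotion. The two scores will tend to agree even if mobilization changes nothing. Separating dose from capacity requires at least some measure of function in the model, and the planned set has none.

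The SAP is not consistent on this. In section 3 it accepts that prior function influences daily MQS, because it adjusts that relation for the Barthel Index. In section 2, where MQS is the exposure and function the outcome, the same variable is left out.

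What is at stake is interpretation. The SAP's title and primary aim speak of effects of mobilization dose. In that setting a significant MQS-mmFIM result could easily be taken as evidence of functional benefit, which the planned model cannot supply.

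**Working it through.** **Inputs from the SAP.** N = 150, alpha 0.05, and a correlation of 0.25 between mobilization dose and discharge disposition (Sample Size and Power). Three covariates (Covariate Data), assumed here to apply to the mmFIM models as well. The SAP gives no correlation between MQS and mmFIM, so that figure is an assumption and is varied below.

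**1. The SAP's own figure.** Fisher z: power = Φ(atanh(r)·√(N − 3 − k) − 1.96), where k is the number of covariates (two-sided, adding the negligible opposite tail). With r = 0.25, N = 150 and k = 0: 0.2554 × √147 = 3.097, and Φ(3.097 − 1.96) = 0.872. The stated power above 0.8 is reproduced. 80% power needs 124 patients.

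**2. Chance of a significant MQS-mmFIM result with no mobilization effect.** Same formula with k = 3, so √144 = 12. Here r is the partial correlation left by shared capacity after adjustment.

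| Assumed residual partial r | atanh(r) × 12 | Significant |
|---|---|---|
| 0.10 | 1.204 | 23% |
| 0.20 | 2.433 | 68% |
| 0.25 | 3.065 | 87% |
| 0.30 | 3.714 | 96% |
| 0.40 | 5.084 | >99% |

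A 95% chance needs r of about 0.29. With 120 patients scored it needs about 0.33.

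**3. Where such a residual could come from.** Let one latent capacity load equally (loading a) on mean MQS and mmFIM, let the covariates explain a share R² of capacity, and set the mobilization effect to zero. The partial correlation is then a²(1 − R²)/(1 − a²R²). For a = 0.6 and R² = 0.2 this is 0.288/0.928 = 0.31; for R² = 0.4 it is 0.216/0.856 = 0.25. Share of 1,000 simulated studies significant (N = 150, linear test):

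| Loading | R² = 0 | 0.2 | 0.4 | 0.6 |
|---|---|---|---|---|
| 0.3 | 20% | 14% | 10% | 7% |
| 0.5 | 89% | 73% | 53% | 29% |
| 0.6 | 99.5% | 97% | 88.5% | 63% |
| 0.7 | 100% | 100% | 99.6% | 93% |

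Reading across a row shows what a further covariate can do. It lowers the rate, but with strong sharing it does not bring it near 5%.

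**4. A model closer to the instruments.** MQS was simulated as daily level times duration, with duration independent of capacity, and mmFIM as two bounded ordinal items (400 repetitions, R² of 0.2 and 0.5). With raw r about 0.38, a linear test was significant in 83-99% of studies and a count model in 39-91%. With raw r about 0.15, the figures were 15-34% and 0.5-5%. The count model had its dispersion fixed near zero, which is conservative for a bounded, underdispersed score.

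**5. Does the shared last day drive it?** In a further model with no mobilization effect, capacity drifts 0.4 SD per day, daily MQS noise is 1 SD, mmFIM noise is 0.5 SD and median stay is 5 days. The correlation was 0.82 with all days, 0.76 without the last ICU day and 0.68 with days 1-3 only. These values depend on the assumed settings. The pattern shows that most of the association comes from shared capacity and survives a lag.

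**The case against.** A reader might infer that a significant result is near-certain, or that the two instruments simply measure the same mobility at the same moment. The documents support neither.

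- *Near-certainty* requires a residual partial correlation of about 0.3 or more, which the SAP does not give. At 0.10 to 0.20 the chance is 23% to 68%, and the planned count model may lower it further.
- *Same measurement* goes too far. MQS is a whole-stay mean, reflects mobilization provided by nurses and therapists, and includes duration. Step 5 also shows that timing overlap is not the main driver.

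It can also be said that for mmFIM the SAP speaks only of prediction and association, and that shared capacity does not invalidate a prediction. That stands: the SAP does not itself claim that dose improves mmFIM. Severity and muscle status are not ignored either, since APACHE2, PSS morbidity and admission RFCSA may absorb part of capacity. The outcome is a non-key secondary, and nothing in the plan becomes unworkable.

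Finally, the Barthel Index describes function before the ICU course and cannot capture capacity after surgery or recovery during the stay. That also stands, and it limits what the fix can achieve. None of these points lets the planned model separate dose from capacity.

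**Conclusion.** The point holds as a limit on interpretation and as an omission in the adjustment set. An MQS-mmFIM association at ICU discharge is likely to reflect shared patient capacity in part and cannot be read as an effect of mobilization dose. With no such effect, the chance of a significant result runs from about 23% to 96% as the assumed residual partial correlation goes from 0.10 to 0.30. The SAP's only correlation, 0.25, concerns discharge disposition. A similar residual between two mobility ratings is plausible but remains an assumption.

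mmFIM at hospital discharge is scored after the exposure window, so it shares the confounding by capacity but not the same-time overlap. The primary analysis, the key secondary comparison and the sample size are not touched.

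**What to change.** 1. Add the Barthel Index to the mmFIM models at ICU and at hospital discharge, and name the full covariate set in the negative binomial sentence. State which Barthel assessment is meant: section 3 places it at hospital admission, Data collection two weeks before.
2. State that the ICU-discharge result is a concurrent association bearing on the construct validity of MQS, and is not evidence of functional benefit.
3. Optionally, add MQS from an early window (for example days 1-3) as a sensitivity analysis. It changes the question asked and is not a cure (step 5).
4. Confirm that mmFIM is recorded at hospital discharge. The data summary lists it only under ICU Discharge.

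Cost: some wording and one model term using a variable already collected. One fewer secondary outcome can then be used as evidence of benefit. Because the Barthel Index precedes the ICU course, residual confounding remains and should be acknowledged in the report.
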